6.1.2.5 Proportion of children who completed referral as reported at Day 7 follow-up

A referral will be considered completed if a child attended a hospital, whether he/she was admitted or not. Children will be counted in the numerator if they received a referral advice (as per definition above) and their caregiver reported to have sought care in a hospital and the follow-up date is within 7 days of Day 0, considering a + 3 days window (10th day included). The denominator will be all children recruited.

Additionally, the proportion will be calculated and reported using only children who were referred as denominator.

Children for whom no Day7 data are available or withdrew prematurely from the study will be assumed not attending a hospital by Day7.

6.1.2.6 Proportion of children with non-severe disease referred to a higher level of care on Day 0

Children with non-severe disease who received a referral advice (as per definition above) at Day0 will be counted in the numerator. The denominator will be all children recruited. Non-severe disease will be defined in a separate document.

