6.1.2 Senegal

Setting

Health posts (HPs) in the Thiès region.

Services & Staffing

Health posts are open between 8 am and 4 pm. They offer primary health services like prenatal care, births, nutrition assessment, immunization, care for sick babies etc. They are staffed with 4 to 5 health care providers on average. No inpatient care for children or adults. No permanent staff for nights and weekends, but nurses may be contacted if needed.

Referral system & O₂ availability

The HPs refer to health centers and health centers refer to hospital level 1, 2 or 3. From HPs, generally only non-medicalized ambulances are available. Oxygen is available in most referral health centers but still of limited use. Most HPs do not have oxygen yet. Pulse oximeters are used in some health centers and not in HPs, except for sites enrolled in the Oxygen Access project led by Air Liquide.

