6.4 Outcomes

6.4.1 Quasi-experimental pre-post study

Two primary outcomes will be assessed between the pre-intervention and post- intervention period:

- ξ Proportion of children referred by a primary care healthcare provider to a higher level of care (either to a hospital or to an inpatient part of a larger primary healthcare facility) at Day 0 consultation
- ξ Proportion of children prescribed an antibiotic at Day 0 primary care consultation

These two outcomes are selected to reflect the intended impact on referral of children with severe disease (pulse oximetry and CDSA) and antimicrobial stewardship (CDSA). Severe complication outcomes are included in secondary outcomes rather than primary as, given the pre-post nature of the study, change in mortality / morbidity outcomes could be influenced by other events occurring between the baseline and post-intervention comparison phase.

Secondary outcomes:

- ξ Proportion of children with a severe complication (death or secondary hospitalisation) by Day 7
 - Secondary hospitalisation refers to any delayed hospitalisation (occurring at any point greater than 24 hours after Day 0 consultation) and any hospitalisation occurring without referral. The denominator is all enrolled children
- ξ Proportion of children admitted to hospital within 24 hours of the Day 0 primary care consultation and as a result of a referral
 - This is used as a proxy for 'appropriate referral' of children, as those with severe disease should generally be admitted to hospital. The denominator for this outcome is also all children enrolled in the study, rather than only referred children. This is because the proportion of referred children that are admitted may be high in routine care, in the context of an inappropriately low referral rate. The aim of the intervention is therefore to increase the overall referral rate of children with severe disease. Hospital admission is chosen as the proxy of severe disease rather than using primary care classification of severe disease, as there are inadequacies in the classification of severe disease in routine practice
- ξ Proportion of children who completed referral as reported at day 7 follow-up
- ξ Proportion of children cured (defined as caregiver reported recovery from illness) at Day 7 follow-up

Sub-groups for analysis of primary and secondary outcomes:

- ξ Age (under 2 months, 2 – 12 months, 13 – 59 months)
- ξ Sex
- ξ Presentation with cough / difficulty breathing

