Additionally, visit information from government-designated hospital records will be collected retrospectively for children whose caregiver reported at Day 7 phone follow-up that they attended hospital, including clinical assessment on arrival (vital signs, admitting diagnosis), admission details (duration, if oxygen was administered, intensive care admission) and admission outcome (final diagnosis, discharge against medical advice, death). The same data will be collected for children who attended a non-hospital higher-level of care (emergency or admission unit of a primary or secondary care facility).

It is expected that some participants may present at the same or another health facility enrolled in the study during the follow-up period. These visits and the findings will be recorded on the appropriate scheduled / unscheduled visit eCRFs.

[figure not shown]
[figure not shown]
[figure not shown]

Fig. 5. Flowchart of the pre-post study. CDSA = Clinical Decision Support Algorithm. CG = Caregiver. HCP = Healthcare provider. OPD = Out-patient department.

Tab. 4. Schedule of the visits and associated CRFs for the pre-post study. The different types of staff collecting data are represented by the following icons:

Research assistant rotating
between different referral health
facilities

Call centre-based research assistant

		Health facility baseline visit		Higher level of care visit ^{1,2}		Follow-up or unscheduled visit at enrolled health facility		Phone follow-up
		Time point		Day 0		Day 0-7		Day 7 [7 - 10]
		Data collection method		Prospective data collection		Review of medical records		Phone interviews
		Study phase		Pre	Post ³			Pre
Events		Forms						Post ³
Informed consent				-				
Screening				TIMCI-01				
Identification & contact information	Full identification	TIMCI-02a						
	Contact information	TIMCI-02b						
	Identification and contact information check	TIMCI-02c						
	Referral facility identification	TIMCI-02d						
	Follow-up identification check	TIMCI-02e						
Socio-demographics		TIMCI-03						
Visit info	Care seeking behaviour, transport and costs for visiting health facility reported by caregiver	TIMCI-04a						
	Visit and admission info recorded by referral facility (medical records, registries) ²	TIMCI-04b						
	Patient journey reported by caregiver at follow-up	TIMCI-04c						
Clinical presentation & medical history	Clinical presentation and medical history reported by caregiver at baseline	TIMCI-05a						

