	Medical history recorded in clinical notes and / or facility registries	TIMCI-05b						
	Chief complaints and medical history recorded in CDSA	TIMCI-05c						

Basic measurements & physical exams	Basic measurements and physical exams recorded in clinical notes and / or facility registries	TIMCI-06a						
	Basic measurements and physical exams recorded in CDSA	TIMCI-06b						
Respiratory rate & pulse oximetry	Respiratory rate and pulse oximetry recorded in clinical notes and/or facility registries ²	TIMCI-07a						
	Respiratory rate and pulse oximetry recorded in CDSA ²	TIMCI-07b						
Laboratory investigations	Respiratory rate and oxygen saturation recorded at arrival by referral facility ²	TIMCI-07c						
	Laboratory investigations recorded in clinical notes and / or facility registries ²	TIMCI-08a						
Diagnosis & care management	Laboratory investigations recorded in CDSA ²	TIMCI-08b						
	Diagnosis and care management in clinical notes and / or facility registries (medical records, discharge summaries)	TIMCI-09a						
	Diagnosis and care management recorded in CDSA	TIMCI-09b						
	Diagnosis and care management recorded by referral facility (medical records, discharge summaries)	TIMCI-09c						
Follow-up at Day 7		TIMCI-10						

¹ Data will be collected retrospectively for visits at facilities offering a higher level of care, including district hospitals, any study facility receiving referrals or admitting patients. ² If appropriate for clinical management.

³ The schedule assumes the intervention includes pulse oximetry plus CDSA.

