6.6.1 Quasi-experimental pre-post study

The sample size for the quasi-experimental pre-post study is calculated separately for each country, based on comparison between pre- and post-intervention periods.. The following assumptions are used:

- ξ power 80%
- ξ alpha 0.05
- ξ pre-intervention referral to a higher level of care 3% (based on informal estimates from country research teams and SPA data from various countries), with a minimum detectable difference of 50%
 - We have chosen a large detectable difference for referral from primary care as not all children referred will complete referral, i.e. a 50% increase in referral rate may only result in a 20 – 30% total increase in completed referrals (this will be assessed as a secondary outcome and is therefore not a component of the sample size calculation)
- ξ pre-intervention antibiotic prescription of 60% (based on informal estimates from countries, SPA data and other observational studies)
- ξ intra-cluster correlation coefficient (ICC) of 0.005 for referral and 0.05 for antimicrobial prescription

- ξ Kenya – estimated average cluster size of 230 children / month (assuming a cluster ratio of health centres : dispensaries 1:2, with 100 / month in dispensaries and 500 / month in health centres)
- ξ Senegal – estimated cluster size of 170 children per month (based on DHIS2 data on outpatient consultations in Thies in 2019)

For the referral primary outcome, we therefore initially estimated requiring the following sample size:

- ξ Kenya – 17 facilities, recruiting an average of 690 children per facility in each period, equating to 11,730 children per period
- ξ Senegal – 18 facilities, recruiting an average of 510 children per facility in each period, equating to 9,180 children per period

For the antibiotic prescription primary outcome, this would enable a minimum detectable reduction of 18% in Kenya and Senegal.

Following lower than anticipated recruitment in the pre-intervention period, sample size calculation was revised. As a result, two additional facilities were added per country and the pre-intervention period was extended from an initially anticipated 3 months to a 6 – 8 month period. A decision was also taken to target a post-intervention sample size of at least the same as the pre-intervention sample size, as well as a minimum duration of 9 months post-intervention to allow for stabilisation over time and some seasonal overlap of pre- and post-intervention periods.

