Data that will be collected at Day 7 follow-up will include cure status (recovery from illness as reported by the caregiver), hospitalisation and death between Day 0 and Day 7. If appropriate, name of the referral facility and duration of hospitalization will be collected to facilitate the retrospective data collection at referral hospital level.

Higher level of care visit

Data collection at this level of care will be conducted retrospectively. A quantitative research assistant using the EDC mobile application will collect data from referral facility records, registries and discharge summaries for children whose caregiver reported at Day 7 phone follow-up that they attended a government-designated referral facility between Day 0 and Day 7. This includes attendance to hospital or emergency / inpatient area of a larger primary or secondary care facility (e.g., study facilities that can admit paediatric patients). Personally identifiable information will be collected to cross-check the identity of the patients. Arrival date and time, basic clinical information on arrival and, if admitted, admission and discharge diagnosis and admission duration will be collected. If available, data on oxygen saturation at admission, oxygen administration and intensive care unit (ICU) admission and duration will also be recorded.

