6.1.1 General definitions

Day 7 assessment

Day 7 assessment refers to information reported by the caregiver after Day 0 and recorded in Day 7 form. Data collected as part of unscheduled visits are also integrated in these forms. If multiple successful follow-up assessments for the same child are recorded within the Day7 database, the most recent follow-up assessment will be used. To limit potential recall bias, assessments conducted far beyond the expected follow-up time will be dropped, i.e. 30 days from Day 0.

Death

A child will be considered deceased if, from Day 7 assessment, his/her status at the time of follow-up is “deceased”. In case of implausible death date (i.e. prior to enrolment date), death will be assumed to be within 7 days of Day0.

Hospitalisation

A child will be considered hospitalised if, from Day 7 assessment, he/she went to a hospital, was admitted overnight or if his/her status at the time of follow-up is “hospitalised”. In case of implausible hospitalisation date (i.e. prior to enrolment date), hospitalisation will be assumed to be within 7 days but after 24hrs of Day0.

Hospitalisation within 24hrs of Day0

For the purpose of primary analysis, a child will be considered admitted to hospital within 24hrs of Day0 consultation if the date of hospitalisation is the same as Day0 date or is one day after Day0 date.

Referral

A child will be considered to be referred (either to a hospital or to an inpatient part of a larger primary healthcare facility) if, at Day0, the research assistant confirms that an urgent referral advice was recorded for the child. If urgency is unknown, referral will be assumed to be urgent.

Antibiotics

Antibiotics will be defined in accordance with the WHO antibiotic point prevalence survey (PPS) methodology [4, 5, 6] and therefore only antibacterials for systemic use will be taken into account.

SpO2 values

SpO₂ should be recorded during the Day0. For the outcomes, the following measures will be taken for spurious and missing SpO₂ values:

- If SpO₂ value is not available, the child will be assumed normoxaemic
- If $70 \leq \text{SpO}_2 < 90\%$, the child will be assumed (with accuracy) to have severe hypoxaemia
- If $40 \leq \text{SpO}_2 < 70\%$, the child will be assumed (with low accuracy) to have severe hypoxaemia
- If $\text{SpO}_2 < 40\%$, the value will be considered spurious (e.g. due to incorrect dataentry) and treated as not available, i.e. the child will be assumed normoxaemic.

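### Completed referral is credited only for attendance at a hospital, although the referral it follows may be to a non-hospital site

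*SAP*

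**What the plan says.** **Completion.** SAP 6.1.2.5 gives the rule: "A referral will be considered completed if a child attended a hospital, whether he/she was admitted or not". The numerator requires referral advice at Day 0, under the SAP's own referral definition, plus a caregiver report of care sought in a hospital, with follow-up no later than day 10. The proportion is reported over all recruited children and again over referred children. Children without Day 7 data count as not having attended.

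**Referral.** SAP 6.1.1 defines it as "either to a hospital or to an inpatient part of a larger primary healthcare facility". The first primary outcome in Protocol 6.4.1 names the same two destinations. The completed-referral outcome in Protocol 6.4.1 carries no restriction to hospitals.

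**Pathway and data collection.** In Senegal the study sites are health posts, and Protocol 6.1.2 says: "The HPs refer to health centers and health centers refer to hospital level 1, 2 or 3". Protocol 6.5.1 plans the same retrospective record collection for children seen at higher-level care outside a hospital. The first footnote to Protocol Table 4 covers "facilities offering a higher level of care, including district hospitals, any study facility receiving referrals or admitting patients". Protocol 7.1.1 says of referral-facility attendance: "This includes attendance to hospital or emergency / inpatient area of a larger primary or secondary care facility".

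**Other Day 7 visits.** In their Day 7 form route, SAP 6.1.6.1 and 6.1.6.2 count visits to facilities other than hospitals as scheduled or unscheduled follow-up.

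**The concern.** The destinations that make a child referred are wider than those that make the referral complete. The narrowing appears only in SAP 6.1.2.5, and no reason is given. A child sent to a health centre or to the inpatient unit of a larger primary facility, who goes there, is a non-completer unless that site is coded as a hospital. The same visit can then be counted as follow-up attendance through the Day 7 form route of SAP 6.1.6, which does not exclude referral visits.

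Completed referral is one of four secondary outcomes. It shows whether more referral advice means more children reaching higher-level care. The protocol relies on that distinction when it justifies its large detectable difference: "a 50% increase in referral rate may only result in a 20 – 30% total increase in completed referrals" (Protocol 6.6.1). If compliant children are missed, the planned analysis cannot separate non-compliance from facility coding. The sensitivity analyses in SAP 6.2.4 vary first encounters, referral definition, study period and hospitalisation timing; none varies destination.

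**Working it through.** **1. Destinations side by side**

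| Destination | Referral | Completion (SAP 6.1.2.5) |
|---|---|---|
| Hospital | Yes (SAP 6.1.1, Protocol 6.4.1) | Yes |
| Inpatient part of a larger primary facility | Yes (same sections) | Only if coded as a hospital |
| Health centre, Senegal | Documented first step (Protocol 6.1.2) | Only if coded as a hospital |

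SAP 6.1.6 uses non-hospital visits as a separate Day 7 category, so the Day 7 data distinguish the two kinds of visit. Nothing in either document says that health centres or inpatient units are coded as hospitals.

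**2. Effect on the outcome.** The plan gives no figure for completed referral, so there is none to reproduce. Let c be true completion among referred children and h the share of completers who went to a site not coded as a hospital. Both are assumptions.

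Measured completion among referred children = c × (1 − h)

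- c = 60%: h = 25%, 50%, 75% gives 45%, 30%, 15%.
- h = 50%: c = 40% gives 20%; c = 80% gives 40%.

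**3. Change among all children.** Inputs from Protocol 6.6.1 are 3% baseline referral and a 20–30% rise in completed referrals. Baseline c = 60% is assumed.

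- Pre: 3% × 0.60 = 1.80%.
- Post: 1.80% × 1.20 = 2.16%; 1.80% × 1.30 = 2.34%.
- True change: +0.36 to +0.54 percentage points.

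The 60% applies to the pre-intervention period only. With referral at 4.5%, post-intervention completion would be 2.16/4.5 = 48% to 2.34/4.5 = 52%.

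With constant h, the measured change is the true change × (1 − h):

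| h | Measured change (points) | OR, +20% | OR, +30% |
|---|---|---|---|
| 0 | +0.36 to +0.54 | 1.204 | 1.307 |
| 25% | +0.27 to +0.41 | 1.203 | 1.305 |
| 50% | +0.18 to +0.27 | 1.202 | 1.304 |
| 75% | +0.09 to +0.14 | 1.201 | 1.302 |

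**4. If h differs between periods.** The measured ratio of proportions = true ratio × (1 − h post)/(1 − h pre). With assumed values:

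- h falling from 50% to 30%: factor 0.7/0.5 = 1.40, so true ratios of 1.20 and 1.30 read 1.68 and 1.82.
- h rising from 30% to 50%: factor 0.5/0.7 = 0.714, so they read 0.86 and 0.93.

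**5. A separate wording point in SAP 6.1.2.1.** The severe-complication numerator takes a hospitalisation if the child was not referred, or if admission fell after 24 hours and within 7 days. Read literally, unreferred children have no 7-day limit. SAP 6.1.1 drops Day 7 assessments only beyond 30 days, so a later admission could enter an outcome defined by Day 7.

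**The case against.** The strongest reply is that the error depends on a form the documents do not show. The Day 7 questionnaire may already code referral health centres and inpatient units as hospitals. The documents also use the word loosely: Protocol 6.1.1 describes Kenyan health centres as small hospitals, and Protocol 7.2.4 speaks of children reported to have attended hospital when describing the search that Protocol 7.1.1 extends to emergency and inpatient areas of other facilities. This stands as a limit: misclassification is not demonstrated. It does not rescue the text, because Protocol 6.5.1 separates hospital from non-hospital higher-level care and SAP 6.1.6 separates hospital from non-hospital visits. On either coding, SAP 6.1.2.5 needs to say what counts.

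The facility name is requested at the follow-up call (Protocol 7.2.4), so much of the information may be recoverable. That is true of the data, but the planned analysis does not use it.

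The sizes are assumed, the odds ratio is stable under constant h, and the primary outcomes are untouched. All of this stands.

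Finally, counting any health-centre attendance would go beyond the inpatient wording of the referral definition. That is a fair caution, and the investigators should state their choice. However, SAP 6.1.2.5 counts hospital attendance without admission, so requiring admission elsewhere would be a stricter test.

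**Conclusion.** The concern holds. SAP 6.1.2.5 is narrower than the referral definition it relies on and narrower than Senegal's documented pathway. Applied as written, it understates completion among referred children and the absolute change between periods, each by the factor (1 − h), unless the Day 7 codes treat these sites as hospitals. The documents give neither h nor true completion, so the size cannot be determined and the figures above are illustrations. The effect is most plausible in Senegal; Kenya is less clear. The odds ratio is safe only if h is constant, which nothing in the plan assures.

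This should be corrected before analysis, but it is confined to one secondary outcome and, through SAP 6.1.6, to follow-up outcomes of lesser rank. Both primary outcomes are measured at Day 0 and are not affected. Confidence is medium because the coding is unseen. The wording point in SAP 6.1.2.1 is independent of this and is also valid.

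**What to change.** - **SAP 6.1.2.5:** count attendance at any destination covered by the referral definition and the country's documented referral pathway: hospital, referral health centre, or emergency or inpatient unit of a larger facility. List the Day 7 codes that qualify in each country, and use the recorded referral-facility name to resolve unclear cases. Report hospital-only completion as a sensitivity analysis.
- **SAP 6.1.6, Day 7 form route:** do not count the referral visit itself as a follow-up visit, but keep genuine return visits by children who completed referral.
- **SAP 6.1.2.1 (separate correction):** require that the child was either not referred at Day 0 or admitted more than 24 hours after Day 0, and in both cases that admission fell within 7 days of Day 0.

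The cost is rewording and some recoding of Day 7 data; no new data collection is needed. The facility name is collected where appropriate (Protocol 7.1.1) and used where available (Protocol 7.2.4), so children whose non-hospital destination was not recorded cannot be recovered. Their number should be reported by country and period.

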The validity of quantitative data will be ensured through data definitions and field restrictions in the electronic systems. Acceptable error rates in critical quantitative data will be established during the pilot phase and documented in the DMP. Pre-defined automated high-frequency checks will be performed including checks of completeness and indicators of other irregularities such as completion time. Reports will be shared with individual quantitative research assistants and their supervisors. In addition to reviewing automatically generated reports for their supervisees, supervisors will perform random accuracy checks of research data compared to available source data. In the pre-post study, quantitative research assistants responsible for the Day 7 call will be audited through random checks of phone logs and repeat phone calls. After confirmation that the study databases contain all expected data, an internal review will check their accuracy and quality. Once all the required data quality assurance and control have been completed and passed, the study databases will be “locked”.

During the pilot phase, qualitative tools will be translated and back translated, and tested using cognitive interviewing to ensure questions asked are understood as intended and felt to be

appropriate. Regular quality checks of transcriptions and translations will be conducted by the qualitative researcher in each country.

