6.1.2 Health, hospitalisation and referral outcomes

6.1.2.1 Proportion of children with a severe complication by Day 7

Severe complication is defined as death or secondary hospitalisation. Secondary hospitalisation refers to any delayed hospitalisation (occurring at any point greater than 24hrs after the Day 0 consultation) and any hospitalisation occurring without a referral. Information on death and hospitalisation will be taken from Day7 follow-up assessment.

Death will be counted in the numerator if death date is within 7 days of Day0 (7th day included). Hospitalisation will be counted in the numerator if the child was not referred at Day0 or hospital admission date is within 7 days of Day0 (7th day included) but after 24hrs of Day0.

The denominator will be all children recruited. Children for whom no death and hospitalisation data are available or withdrew prematurely from the study will be assumed to be alive and not hospitalised by Day7.

6.1.2.2 Proportion of children admitted to hospital within 24 hours of Day 0 consultation and as a result of a referral

Information on hospitalisation will be taken from Day7 follow-up assessment.

Hospitalisation will be counted in the numerator only if the child received a referral advice (as per definition above) at Day0 and hospital admission date is within the end of the following day. The denominator will be all children recruited.

Additionally, the proportion will be calculated and reported using only children who were referred as denominator.

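### SAP 6.1.2.5 times referral completion by the phone call, so a referred child admitted on Day 0-1 but reached after Day 10 counts in 6.1.2.2 and fails in 6.1.2.5

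*SAP*

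**What the plan says.** Referral completion is a named secondary outcome (Protocol 6.4.1; SAP 3.1.4). SAP 6.1.2.5 first gives the concept: "A referral will be considered completed if a child attended a hospital, whether he/she was admitted or not". The numerator then requires referral advice at Day 0 and that the caregiver "reported to have sought care in a hospital and the follow-up date is within 7 days of Day 0", extended by three days so that Day 10 is the last day allowed. The main denominator is all recruited children. In addition, "the proportion will be calculated and reported using only children who were referred as denominator". For absent data the rule is: "Children for whom no Day7 data are available or withdrew prematurely from the study will be assumed not attending a hospital by Day7".

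Three other places bear on this:

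- SAP 6.1.1 on late contacts: "assessments conducted far beyond the expected follow-up time will be dropped, i.e. 30 days from Day 0". Where a child has several successful contacts, the latest is used.
- SAP 6.1.2.2, admission within 24 hours following referral: the child counts if referred and "hospital admission date is within the end of the following day". No condition is placed on the date of the call.
- Protocol 7.1.1 and SAP 3.8: the Day 7 call has a window of Day 7 to Day 10.

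**The concern.** Hospital attendance is a past event, and a caregiver reached on Day 12 can report it. The rule in 6.1.2.5 does not ask when the child attended. It asks when the caregiver was reached, and treats a late contact as a failure to complete. This is not a missing-data rule: the information exists, was retained under 6.1.1 and reports attendance, yet the child stays in the denominator and leaves the numerator.

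Two things are at stake. The first is coherence. Every child admitted as a result of a referral has completed that referral, so the 6.1.2.2 numerator should be a subset of the 6.1.2.5 numerator, and as written it need not be. The second is the pre-post comparison. Late calls with no recorded exception can only remove completers whose attendance was timely. If the share of late calls differs between periods, part of the apparent change in completion is a change in call timeliness. Protocol 6.6.1 gives this outcome some weight: it justifies the 50% referral difference by expecting only a 20-30% rise in completed referrals, to be assessed as a secondary outcome.

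**Working it through.** The SAP states no figure for this outcome, so there is none to reproduce. The check applies the written rules to test cases and then sizes the effect under stated assumptions.

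**Which date is tested.** SAP 6.1.6.1 and 6.1.6.2 use the Day 7 follow-up date with the same Day 10 limit, and Protocol 7.1.1 gives Day 7 to Day 10 as the phone window. The follow-up date in 6.1.2.5 is therefore the contact date.

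**Test cases.** A referred child who attended and was admitted on the day shown, judged on the latest assessment (Day 30 read as kept):

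| Admitted | Call | 6.1.2.2 | 6.1.2.5 as written | By event date, to Day 7 | By event date, to Day 10 |
|---|---|---|---|---|---|
| Day 0 | Day 8 or 10 | yes | yes | yes | yes |
| Day 0 | Day 11, 12 or 30 | yes | **no** | yes | yes |
| Day 0 | Day 31 (dropped) | no | no | no | no |
| Day 9 | Day 10 | no | yes | no | yes |

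The second row is the contradiction. The last row shows that the choice of window for an event-date rule also matters.

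**Size within a period.** Inputs: referral r = 3% (planning value, SAP 3.4); completion c = 60% and late-call share L = 2-10% (assumptions; neither is in the documents). L is the share of completers whose latest retained contact falls after Day 10.

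- Loss among referred children = c × L: 0.60 × 0.02 = 1.2 points; 0.60 × 0.10 = 6.0 points.
- Loss among all recruited children = r × c × L: 0.03 × 0.60 × 0.02 = 0.036, about 0.04 points; 0.03 × 0.60 × 0.10 = 0.18 points. The true value is 0.03 × 0.60 = 1.8%.
- With c from 40% to 80%, the range is 0.03 × 0.40 × 0.02 = 0.024 points to 0.03 × 0.80 × 0.10 = 0.24 points.
- In Kenya at the initially planned 11,730 children per period: 11,730 × 0.03 × 0.60 = 211 completers, of whom about 4 (2%) to 21 (10%) would be scored as failures.

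**Size between periods.** Observed ratio = true ratio × (1 − L post) / (1 − L pre). Take referral rising from 3% to 4.5% with completion constant, so the true ratio is 1.50:

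- Equal shares: 1.50, unchanged. The risk difference, which SAP 6.2.1 also reports, shrinks by the factor 1 − L; at 10% late it goes from 2.7 − 1.8 = 0.90 to 0.81 points.
- 10% pre, 2% post: 1.50 × 0.98 / 0.90 = 1.63.
- 2% pre, 10% post: 1.50 × 0.90 / 0.98 = 1.38.
- Wider range, 20% pre and 5% post: 1.50 × 0.95 / 0.80 = 1.78. Reversed: 1.50 × 0.80 / 0.95 = 1.26.

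**The case against.** The strongest reply is that the window follows from the outcome's name. Completion is to be reported at Day 7 follow-up, that follow-up has a three-day window, and the SAP puts the same limit on scheduled and unscheduled visits taken from the Day 7 form. It looks like a deliberate convention. That is fair as an account of its origin, but it does not remove the conflict with 6.1.2.2, which draws on the same retained assessments without the limit.

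A second reply concerns data, and it stands. Completion includes attendance without admission. The Day 7 items listed in Protocol 7.1.1 show no attendance date for such children, and arrival dates come from the records of government-designated facilities. For an undated attendance, the call limit is what bounds the event in time. Accepting every attendance reported up to Day 30 would give late-called children longer to qualify.

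Third, calls are scheduled to end about Day 10: one call, then attempts on the next three days. The 30-day rule shows that later contacts are anticipated, not that they are common.

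A reader might also infer more than the documents support:

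- That audit calls push known completers out of the window, because staff are "audited through random checks of phone logs and repeat phone calls" and the latest assessment is used. Nothing says that audit calls enter the Day 7 database.
- That the pre-post comparison is biased. That bias in the ratio needs unequal late-call shares, and neither share is given.
- That all the other hospital outcomes are timed by event date. In 6.1.2.1, as worded, hospitalisation of a child who was not referred carries no date condition.

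**Conclusion.** The inconsistency is real and follows from the text alone; one retained late call reporting a Day 0-1 admission after referral is enough to produce it. Two secondary outcomes then disagree about the same child, and a known completer is counted as a failure.

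Its frequency, and so its size, is unknown. Under the assumptions above (60% completion, 2-10% late calls, 3% referral) the loss is about 0.04-0.18 points on the main denominator. The 1.2-6.0 points among referred children are the same relative loss of 2-10% on the additional denominator and should not be read as the effect on the main outcome. Distortion of the pre-post ratio is possible but conditional on call timeliness changing between periods. The primary outcomes are recorded at Day 0 and are not touched, and secondary outcomes are modelled only if numbers allow. The point is worth correcting because the correction is cheap, not because the effect is shown to be large.

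**What to change.** Amend SAP 6.1.2.5 as follows:

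1. Count a referred child as a completer if any retained assessment (up to Day 30) reports a hospital admission or attendance whose recorded date falls within the outcome window, whatever the date of the call. Every child in the 6.1.2.2 numerator is then also a completer. Because this reads any retained assessment, it needs a stated exception to the latest-assessment rule in 6.1.1.
2. State whether the window ends on Day 7 or Day 10. The section's own default for missing data speaks of Day 7, while its call limit is Day 10.
3. Keep the Day 10 call limit only for attendances with no recorded date.
4. Report a sensitivity analysis that accepts attendance from all retained assessments, and tabulate the number of contacts after Day 10 by period, so that the size of the problem can be seen.

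The cost is a short SAP edit and a small code change, with no new data. There are two downsides. Recall is slightly longer for late calls, which 6.1.2.2 already accepts. If Day 7 is chosen, attendances on Days 8-10 that now count leave the numerator. Undated attendances reported after Day 10 remain scored as failures in the main analysis; the sensitivity analysis shows how much they matter.
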